- ^f Where chemistry labs indicated, the following serum tests are to be performed: Chem 7 (sodium, potassium, bicarbonate, BUN, creatinine, glucose), ALT, AST, total bilirubin, alkaline phosphatase, amylase, creatine kinase (CK), TSH (thyroid stimulating hormone), LDH and cortisol (cortisol only required on treatment days and not at screening, EOT or 28 day follow up)
- g Procedures for cycle 5 day 1 ONLY can be +/- 7 days of this visit, NaF PET/CT scans to be done prior to biopsy for patients receiving biopsy
- ^h Can be +/- 7 days of this visit
- ⁱ Can be +/- 7 days of this visit, and not required if this is off-study visit and previous scans already confirmed disease progression ^j CT of chest at this time point only as clinically indicated
- ^k PT/INR and PTT only required for those subjects who will be undergoing a biopsy and only required at biopsy timepoints (screening and C5D1). May be performed up to 7 days prior to biopsy, required same day if subject is on coumadin. PT and/or INR may be done.
- ¹ If NaF PET/CT is available as standard of care procedure, this may be substituted for bone scan (bone scintigraphy), however all pre-treatment and post-treatment tests must use the same modality (NaF PET/CT or bone scintigraphy)
- m Biopsy can be performed +/- 14 days of this visit
- ⁿ For Arm 2, Subjects will receive pTVG-AR vaccine on days 1 and 8 of Cycles 1, 2, 5, and 6 and days 1 and 8 of Cycles 1 and 2 of the vaccine booster cycles (if applicable). Subjects will receive pTVG-HP vaccine on days 1 and 8 of Cycles 3, 4, 7, and 8 and days 1 and 8 of Cycles 3 and 4 of the vaccine booster cycles (if applicable).
- °CT of abdomen and pelvis (+/- chest as clinically indicated) and bone scintigraphy continue every ~12 weeks, +/- 7 days from visits at day 1 of cycles 13, 17, 21, 25, and 29
- ^p 100 mL green top tubes and 10 mL red top tubes collected at day 1 of cycles 13 and 17.
- ^q Blood for immune analysis only collected if not previously collected within 60 days
- MRI imaging may substitute for CT, but the same type of imaging must be used to determine eligibility and progression
- ^s Treatment cycles are defined as 21 days.

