pTVG-AR vaccine, both vaccine(s) and pembrolizumab treatment will be held until the toxicity resolves to Grade 1 or less. If a patient develops a second Grade 3 event (or any Grade 4 event) believed at least possibly related to pTVG-HP or pTVG-AR vaccine, no further treatments will be given. Patients will not have any dose modifications (or change in dose or schedule) of pembrolizumab in this study except as noted in section 8.1. If the toxicity does not resolve, or the criteria for resuming treatment (to Grade 1 or less as in the table below) are not met, the patient will discontinue pembrolizumab (and continuing vaccinations, if the adverse event was not believed to be immune-mediated), or discontinue both study medications (vaccine and pembrolizumab) if the adverse event was considered immune-mediated and the vaccinations were already being held. The patient will remain on study, however, with collection of radiographic and laboratory data as per protocol. The rationale for these modifications is that patients could continue to benefit in terms of anti-tumor response and this could in fact be related to the development of other autoimmune toxicities, and patients who have non-immune related toxicity from pembrolizumab could still potentially benefit from continued DNA vaccination. While rare overall, autoimmune events observed following pembrolizumab treatment of patients with melanoma typically resolved and did not necessarily lead to discontinuation of treatment.

If a subject has to hold treatment for a visit, confirm with the sponsor that the subject should skip the current visit and resume treatment at the next timepoint (i.e. if a subject has to hold drug at C7D1 due to an AE, the patient would skip C7D1, be reevaluated at C7D8 and if necessary to continuing holding, come back and resume treatment at C8D1, if allowable per protocol).

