11. STATISTICAL CONSIDERATIONS

r. Overview

This is a 1:1 randomized, open-label, multi-institution phase II trial designed to evaluate the immunological and clinical effect of one versus two DNA vaccines, used as T-cell activating therapies, and given concurrently with pembrolizumab. The rationale for conducting this trial is summarized in Section 2.

s. Objectives

Primary Objective:

To determine the 6-month progression-free survival rate in patients with metastatic, castration-resistant prostate cancer (mCRPC) treated with pembrolizumab in combination with one versus two DNA vaccines as T-cell activating agents

Secondary Objectives:

- 1. To determine the overall objective response rate (using Prostate Cancer Working Group 3 (PCWG3) criteria)
- 2. To determine the PSA response rate (decline > 50%)
- 3. To determine the median progression-free survival rate
- 4. To determine median duration of PSA and/or objective response in responding individuals
- 5. To determine the overall survival
- 6. To determine whether the development of antigen-specific Th1 immunity elicited with treatment to either antigen (PAP or AR) is associated with PSA response
- 7. To evaluate the safety and tolerability of pTVG-HP DNA vaccine with or without pTVG-AR DNA vaccine and pembrolizumab

Exploratory Objectives:

- 1. To evaluate PAP-specific and AR-specific antibody responses following treatment with pembrolizumab and DNA vaccine(s)
- 2. To determine whether treatment with either sequence elicits immunologic antigen spread to other prostate associated antigens
- 3. To determine whether pre-existing antigen-specific immunity is predictive of immunological or objective clinical response
- 4. To determine, in a subset of patients, whether early changes in bone observed by NaF PET/CT are associated with immunological or objective clinical response, or pathological changes associated with immune-cell infiltration
- 5. To determine second PSA response rates in patients treated in follow-on courses
- 6. To determine whether treatment elicits changes in the gut microbiota composition
- 7. To determine whether changes in gut microbiota are associated with clinical response (PSA decline > 50%)

t. Study Design

The study is designed as a randomized, two-arm, open-label, multi-institution phase 2 trial. Study arms will be defined as follows:

Course 1:

Arm 1: 100 μg pTVG-HP administered intradermally (i.d.) days 1, 8 + 200 mg

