The ITT population consists of all patients who are randomized. The per-protocol population consists of all evaluable patients, i.e., patients who have been treated according to protocol (all inclusion/exclusion criteria are satisfied, and adequate treatment compliance (complete treatment with pTVG-HP DNA vaccine alone or in combination with pTVG-AR DNA vaccine and Pembrolizumab to at least week 12). The safety population consists of all subjects who received at least one dose of pTVG-HP DNA vaccine with or without pTVG-AR DNA vaccine and Pembrolizumab. All primary, secondary and correlative outcomes will be analyzed for both the IIT and per-protocol population. The IIT population will be the primary analysis population. Safety will be evaluated using the safety population.

To attain 60 evaluable participants, the trial may randomize more than 60 participants if any are deemed unevaluable.

iii. Baseline Comparability

All measurements (variables) collected at baseline will be summarized and compared between study arms. These include demographic variables, ECOG PS, lab parameters (CBC, chemistry panel, serum testosterone, PSA and PAP) medical history information and CTCs. Comparisons between study arms of baseline variables on a continuous scale will be performed using a two-sample t-test and/or nonparametric Wilcoxon Rank Sum test. Comparisons between study arms of baseline variables on a categorical scale will be performed using a chi-square or Fisher's exact test.

iv. Analysis of Primary Endpoint

The 6-month PFS rate will be calculated for each study arm along with the corresponding two-sided 95% confidence interval which will be constructed using the Wilson score method. Patients who withdraw from the study without a progression or death event before the 6-month assessment will be excluded from this analysis. The stratified (by randomization strata) Mantel-Haenszel test will be used to compare the 6-months PFS rates between study arms.

v. Analysis of Secondary Endpoints

F.5.1. Overall Objective Response Rate and PSA Response Rates

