Subjects will be evaluated at each visit by a review of systems based on the most recent version of the NCI common toxicity criteria. Furthermore, serum chemistries, including renal function tests, blood counts, liver function tests, and serum amylase, will be evaluated at 6-12 week intervals. Toxicities will be summarized by type and severity in tabular format. Toxicity rates (grade 2, grade 3, grade 4, grade \geq 2, grade \geq 3, etc.) will be calculated for each study arm and reported along the corresponding 95% confidence intervals. The 95% confidence intervals will be constructed using the Wilson score method. Fisher's exact test will be used to compare toxicity rates between study arms. Serum chemistry and amylase parameters will be summarized using standard descriptive statistics. Changes from the baseline assessment will be evaluated using a paired t-test.

vi. Exploratory Analyses

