
- 0 No adverse event or within normal limits
- 1 Mild adverse event
- 2 Moderate adverse event
- 3 Severe adverse event
- 4 Life-threatening or disabling adverse event
- 5 Fatal adverse event

All adverse events will be recorded from time of treatment initiation through 30 days after the final dose of study treatment, as well as any time after these 30 days for events that are believed to be at least possibly related to study treatment. Please note: SAEs,

regardless of relationship, occurring from the time of consent until 90 days after the final dose of pembrolizumab will be collected and reported as per section E.1.

Appropriate clinical, diagnostic, and laboratory measures to attempt to delineate the cause of the adverse reaction in question must be performed and the results reported. All tests that reveal an abnormality considered to be drug- or vaccine-related will be repeated at appropriate intervals until the course is determined or a return to normal (or pretreatment) values occurs. Information will be recorded as noted above.

B. Disease Oriented Team Meetings

UWCCC site: This study undergoes review of subject safety at regularly scheduled Disease Oriented Team (DOT) meetings where the following are discussed as applicable: number of subjects enrolled, subject treatments given, dose holds/modifications, significant toxicities, response to treatment, and the subjects' overall status. These discussions are documented in the DOT meeting minutes.

C. UWCCC Data and Safety Monitoring Committee (DSMC) Study Progress Review and Oversight

The review of Protocol Summary Reports (PSRs) enables the UWCCC DSMC to assess whether the study should continue, continue with modifications, be suspended, or be closed. Following their review, the UWCCC DSMC will notify the sponsor-investigator of their recommendation and the authority for continuing, modifying, suspending, or closing the protocol is the responsibility of the applicable sponsor-investigator, Principal Investigator, IRB, FDA or other regulatory authority associated with the protocol.

Based on the risk level of this study, as determined by the UWCCC Protocol Review and Monitoring Committee, PSRs must be submitted to the UWCCC DSMC by the UWCCC site on a quarterly basis.

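### The safety population requires a dose of pTVG-HP, which Arm 2 does not receive until day 43, so Arm 2 patients who stop sooner drop out of the final toxicity analysis

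*Combined protocol and SAP*

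**What the plan says.** Section 11.w.ii defines the safety population as "all subjects who received at least one dose of pTVG-HP DNA vaccine with or without pTVG-AR DNA vaccine and Pembrolizumab" and adds: "Safety will be evaluated using the safety population". Section 11, F.5.4, then plans toxicity rates by arm with Wilson 95% intervals, and states that "Fisher's exact test will be used to compare toxicity rates between study arms".

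The arms receive pTVG-HP on different schedules. Arm 1 receives it in every one of cycles 1 to 8. For Arm 2, footnote n of the Plan of Treatment gives pTVG-AR in cycles 1, 2, 5 and 6, and says: "Subjects will receive pTVG-HP vaccine on days 1 and 8 of Cycles 3, 4, 7, and 8". Sections 6, 9 and 11.t give the same allocation.

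Section 8 contains rules that can end treatment before cycle 3. One covers Grade 4 toxicity, and Grade 3 toxicity when it occurs for the second time; where this is "believed at least possibly related to pTVG-HP or pTVG-AR vaccine, no further treatments will be given". It also stops both pembrolizumab and vaccine after a second Grade 3 or any Grade 4 event attributed to pembrolizumab if that event is immune-related.

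**The concern.** A safety population should contain every patient exposed to study treatment. Here, entry depends on one agent that one arm receives from the first day and the other only in its third cycle. Arm 2 patients must therefore remain on treatment for two full cycles before they count, while vaccinated Arm 1 patients count at once.

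That condition is met or missed after treatment has begun, and toxicity can be the reason it is missed. A Grade 4 event possibly related to pTVG-AR in cycle 1 ends treatment, so the patient never receives pTVG-HP, and the event never enters the Arm 2 rate. Withdrawal, symptomatic deterioration or death before cycle 3 has the same effect on the denominator.

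Safety and tolerability is secondary objective 7, and Section 6 names possible extra toxicity from two vaccines as the particular worry in Arm 2. The final arm comparison could lose some of the patients who bear most directly on that worry.

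**Working it through.** **Inputs from the documents**

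- Cycle length 21 days (Plan of Treatment, footnote s).
- pTVG-HP: Arm 1 from cycle 1 day 1; Arm 2 from cycle 3 day 1 (Plan of Treatment, footnote n for each arm).
- Vaccine on days 1 and 8 of a cycle, pembrolizumab on day 1 (Section 6).
- Planned size 30 per arm (Section 11.v), used only for the illustration.

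**Timing**

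Day of cycle c day 1 = (c − 1) × 21 + 1.

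- Check against the plan: cycle 5 day 1 = 4 × 21 + 1 = day 85, which matches the month-3 day in Section 7.A.
- First pTVG-HP in Arm 2: 2 × 21 + 1 = day 43.
- Exposure before then: 2 cycles × 2 = 4 pTVG-AR doses, and 2 pembrolizumab infusions.

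Day 43 is nominal, since visit windows and held doses can shift it.

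**Who is counted**

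| Patient | Arm 1 | Arm 2 |
|---|---|---|
| Vaccinated, stops for good in cycle 1 or 2 | In | Out |
| Reaches cycle 3 and receives that vaccine dose | In | In |

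**Effect on the reported rate**

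Let x of n treated Arm 2 patients have toxicity, and let k be excluded, t of them with toxicity. The reported rate is (x − t)/(n − k). This is below x/n exactly when n(x − t) < x(n − k), that is, when t/k > x/n. The rate falls if the excluded patients had more toxicity than the arm as a whole, and rises if they had less.

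**Illustration (all counts assumed; none is in the documents)**

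Take x = 9 with Grade 3 or higher toxicity, n = 30: 9/30 = 30.0% (Wilson 95% CI 16.7 to 47.9%).

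| Excluded (k) | All had toxicity | None had toxicity |
|---|---|---|
| 1 | 8/29 = 27.6% | 9/29 = 31.0% |
| 2 | 7/28 = 25.0% | 9/28 = 32.1% |
| 3 | 6/27 = 22.2% (10.6 to 40.8%) | 9/27 = 33.3% (18.6 to 52.2%) |

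For k = 3 the intermediate cases are t = 1: 8/27 = 29.6%, and t = 2: 7/27 = 25.9%. The full range for three exclusions is 22.2 − 30.0 = −7.8 to 33.3 − 30.0 = +3.3 percentage points.

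If Arm 1 had 5/30 (also assumed), the two-sided Fisher p-value would be 0.36 with everyone included. It would be 0.36, 0.53 and 0.74 after excluding one, two or three Arm 2 patients who all had toxicity.

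**The case against.** The strongest reply is that the phrase is shorthand for the two regimens taken together. Objective 7 uses it that way ("To evaluate the safety and tolerability of pTVG-HP DNA vaccine with or without pTVG-AR DNA vaccine and pembrolizumab"), and the per-protocol definition in Section 11.w.ii uses something close to it. On that reading, one dose of the regimen means one dose of study treatment, and an Arm 2 patient enters on day 1. This is probably what was meant, and nothing suggests an intention to leave out patients who received only pTVG-AR. But wording that describes a regimen in an objective becomes a condition when it defines who is counted, and no other text corrects it. The detailed SAP promised in Section 11.w.i could do so, but nothing says that it will.

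A second reply is that a strict parse might also make pembrolizumab a required dose, so Arm 1 could lose patients too. That would reach only an Arm 1 patient who stops between vaccination and the first infusion, which Section 9 places on the same visit after 60 minutes of observation. The imbalance between arms remains.

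A third is that few patients should be affected. Entry requires a life expectancy of at least 6 months, no vaccine-related event above Grade 2 is expected, a first Grade 3 vaccine-related event leads to a hold, and month-3 scans do not by themselves end treatment. This is fair, and it limits the likely size. It does not make the definition right, and in an arm of about 30 each excluded patient matters.

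Finally, the consequences are contained, and this stands in full. The Arm 2 stagger and the stopping boundaries in Section 6, and adverse event recording and DSMC review in Section 13, do not depend on this population.

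**Conclusion.** The concern holds. Followed as written, Section 11.w.ii gives a safety denominator that omits treated Arm 2 patients who stop before about day 43 and keeps the corresponding Arm 1 patients. The final toxicity rates, their intervals and the Fisher comparison all inherit this.

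The timing follows from the plan's own schedule. The size does not: it depends on how many Arm 2 patients stop before cycle 3 and on their toxicity, and the documents give neither. The shift of −7.8 to +3.3 points rests on an assumed 9/30 and three exclusions, and its lower end needs one in ten Arm 2 patients to stop early, all with toxicity. No direction of bias is established.

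This is most likely a drafting slip. It concerns the final analysis of a secondary objective and not the protection of participants. It should be corrected before the final analysis.

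**What to change.** Replace the definition in Section 11.w.ii with one that covers every treated patient: anyone given one or more doses of any study agent, whether pTVG-HP, pTVG-AR or pembrolizumab. Carry the same definition into the detailed SAP. Both arms then enter on day 1 and the 42-day gap in Arm 2 disappears.

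The cost is one sentence. No visit, procedure or data item changes, because Section 13.A already provides that "All adverse events will be recorded from time of treatment initiation through 30 days after the final dose of study treatment". Since the trial is open-label, it is better to make the change now than when the toxicity results are being assembled.

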received vaccines at every 2-week intervals and pembrolizumab at every 3-week intervals. Emerging data from animal studies has suggested that "density" of vaccination (every week rather than every 2 weeks) is preferable for initiating an immune response, but periods of time between booster immunization may be important for establishing immune memory. In order to accommodate these observations into a workable schedule, the current trial will aim for two vaccinations per 3-week cycle with pembrolizumab, and using two such cycles consecutively prior to alternating vaccine. In addition, because most patients with metastatic prostate cancer have bone metastases, a site that is difficult to characterize objectively, a subset of patients treated at the University of Wisconsin Carbone Cancer Center will undergo NaF PET/CT with site-directed biopsies to determine if this modality can identify early metabolic signals associated with immune infiltration as an early treatment biomarker. An exploratory aim will be to determine whether treatment elicits changes in the gut microbiome, and whether clinical response is associated with changes in the composition of the gut microbiome. Based on published studies and our own prior experience, the median time to disease progression in this stage of disease is approximately 3 months. Hence the use of 6-month progression-free survival provides a clinically relevant endpoint, and a basis for comparing the two treatment arms. Patients without progression at 6months will continue with pembrolizumab alone until PSA rise, at which point vaccine courses will be restarted. This approach will permit evaluation of second courses of treatment in responding individual. Overall, identification of PSA responses (defined as PSA decline > 50%), objective radiographic responses, as well as delays in the time to disease progression, will serve as evidence of clinical activity to compare the treatment arms and be used for planning future confirmatory clinical trials.

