pembrolizumab IV day 1 of 21-day cycles x 8 cycles

Arm 2: 100 μg pTVG-AR i.d days 1, 8 + 200 mg pembrolizumab IV day 1 of 21-day cycles,

for cycles 1, 2, 5 and 6 alternating with

100 µg pTVG-HP i.d. days 1, 8 + 200 mg pembrolizumab IV day 1 of 21-day

cycles, for cycles 3, 4, 7 and 8

Patients who have not come off trial at the end of cycle 8 (month 6) will continue to receive pembrolizumab at 3-week intervals, up to a total of 2 years (32 cycles) of treatment, or until evidence of radiographic progression. If prior to 2 years, and in the absence of radiographic progression, patients with rise in PSA (25% over month 6 value and with minimum rise of 2 ng/mL) will resume vaccination in follow-on courses:

Arm 1: 100 μg pTVG-HP i.d. days 1, 8 + 200 mg pembrolizumab IV day 1 of 21-day cycles

x 4 cycles

Arm 2: 100 μg pTVG-AR i.d days 1, 8 + 200 mg pembrolizumab IV day 1 of q 21-day

cycles, for two cycles followed by

100 µg pTVG-HP i.d. days 1, 8 + 200 mg pembrolizumab IV day 1 in 21-day

cycles, for two cycles

Eligible subjects will be randomly assigned in 1:1 fashion to either Arm 1 or Arm 2.

u. Randomization and Stratification

Eligible patients will be randomized to the two study arms with an allocation ratio of 1:1. The randomization will be stratified by institution and prior treatment (or not) with prior second generation AR targeting agents. Treatment arm assignment will be made by biostatics/investigational pharmacy after a patient has been registered.

v. Sample Size and Power Calculation

The expected 6-months PFS rate in Arm 1 (pTVG-HP DNA vaccine and Pembrolizumab) in this patient population is 20-30%. It is hypothesized that adding pTVG-AR DNA vaccine (Arm 2) will increase the 6-months PFS rate to at least 55%. The following table shows the required sample sizes for detecting various differences in the 6-months PFS rates between the two study arms, assuming 80% power and a one-sided 0.10 significance level. As this is a phase II study, a less stringent significance level of 0.10 rather than the traditional 0.05 level will be used for the primary efficacy evaluation.

Required sample sizes to detect a difference of 20-30% vs. 50-60% in the 6-months PFS rates between arms			
	6-mont	hs PFS rate in	ı Arm 2
6-months PFS rate in Arm 1	0.50	0.55	0.60
0.20	54	42	32
0.25	80	58	44
0.30	124	82	58

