A sample size of 60 evaluable patients (30 per arm) is proposed for this study. The following table shows the attainable power levels for detecting various differences in the 6-months PFS rates between arms with a sample size of 30 patients per arm at the one-sided 0.10 significance level.

Attainable power levels for detecting various differences in the 6-months PFS rates					
between arms with the proposed sample siz	e of 30 patients	per arm			
6-months PFS rate in Arm 2					
6-months PFS rate in Arm 1	0.50 0.55 0.60				
0.20	88.8%	94.8%	98.0%		
0.25	77.1%	87.4%	94.1%		
0.30	62.0%	75.8%	86.6%		

Hence, the proposed sample size of 60 evaluable patients will provide 77-98% power to detect an anticipated difference in the 6-months PFS rates of 20-25% in Arm 1 vs. 50-60% in Arm 2. Analogously, the sample size will provide between 62-94% power to detect a difference of 25-30% in Arm 1 vs. 50-60% in Arm 2. PASS software (NCSS, LLC) version 12 was used to conduct the samples size calculations.

w. Analysis

i. General

This section outlines the statistical analysis strategy and procedures for the study. Prior to the analysis of the final study data, a detailed Statistical Analysis Plan (SAP) will be written describing all analyses that will be performed.

Summary tabulations will be presented that will display the number of observations, mean, standard deviation, median, range, minimum, and maximum for continuous variables and the number and percent per category for ordinal and categorical data. All endpoints of this study will be presented graphically where possible using boxplots and histograms for continuous variables and (stacked) bar charts for categorical variables. Data analysis will be performed using SAS® (SAS Institute Inc., Cary, North Carolina) version 9.4 or greater.

There are many comparisons made between the two trial arms for multiple measurements, both clinical and laboratory. However, since this is an early phase efficacy trail, no adjustment will be made for multiple comparisons.

ii. Analysis Populations

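### Per-protocol status requires complete treatment to week 12 with no exception for early failure, so per-protocol PFS rates tend to be inflated and the arm contrast can shift either way

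*Combined protocol and SAP*

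**What the plan says.** Section 11, Analysis Populations, defines the set as follows: "The per-protocol population consists of all evaluable patients, i.e., patients who have been treated according to protocol". The bracket after that sentence adds that eligibility criteria must be met and that the assigned vaccine(s) and pembrolizumab must have been given completely to week 12 or beyond. No exception is made for patients whose treatment ends early because they die, progress or have toxicity.

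The same section makes all randomized patients the ITT population and names ITT as the primary analysis population. It analyses the primary, secondary and correlative outcomes in both sets, and it gives safety its own population.

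The target number is also stated in evaluable patients. Under Sample Size and Power Calculation: "A sample size of 60 evaluable patients (30 per arm) is proposed for this study". Under Analysis Populations: "To attain 60 evaluable participants, the trial may randomize more than 60 participants if any are deemed unevaluable". No expected unevaluable rate and no cap on the number randomized is given.

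Two other places bear on who would be excluded. The Summary in Section 2 says that "the median time to disease progression in this stage of disease is approximately 3 months". Sections 6 and 7 say that progression on the 3-month scan does not by itself end treatment.

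**The concern.** A set chosen by what happens after randomization is no longer protected by randomization. Here the condition is completing 12 weeks of treatment in a disease where progression is expected at a median of about 3 months. Some patients who miss the condition miss it because they failed: they died, or became symptomatic and needed other therapy. Section 7 counts progression and death as PFS events, so deaths and documented progressions that should lower the 6-month rate disappear from the per-protocol denominator.

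Two things are at stake. The per-protocol rate in each arm may look better than the regimen delivers. The per-protocol comparison may also shift if early stopping differs between arms. The protocol raises that possibility itself: Section 6 notes a theoretical chance of more toxicity in Arm 2. A per-protocol result read as confirmation of the ITT result could then reassure, or disagree with it, for the wrong reason.

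**Working it through.** **Inputs from the plan (Section 11, Sample Size and Power Calculation).** Arm 1: "The expected 6-months PFS rate in Arm 1 (pTVG-HP DNA vaccine and Pembrolizumab) in this patient population is 20-30" per cent. Arm 2: the added vaccine "will increase the 6-months PFS rate to at least 55" per cent. Allocation is 1:1 with 30 evaluable patients per arm. The table of required sample sizes is built "assuming 80% power and a one-sided 0.10 significance level", and the power table uses the same level.

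**The plan's own figure.** For 25% vs 55% with 30 per arm, the pooled normal approximation gives

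z = [0.30 × √30 − 1.2816 × √(2 × 0.40 × 0.60)] / √(0.25 × 0.75 + 0.55 × 0.45) = (1.643 − 0.888) / 0.660 = 1.145,

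so power is 87.4%, as stated. The other eight cells of the power table agree within 0.1 point. The check below therefore starts from the plan's own rates.

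**Who can be excluded.** The first scheduled on-treatment scan is at cycle 5 day 1, after 4 × 21 = 84 days, which is week 12 (± 7 days). Progression on that scan does not force stopping. A patient whose only failure is radiographic can thus complete 12 weeks and stay in the set. Those lost are deaths, symptomatic deterioration, toxicity holds or stops, withdrawals, missed doses and eligibility violations.

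**Effect on one arm's rate.** Let p be the true 6-month PFS rate and e the share of randomized patients excluded, all of whom would have failed by month 6. The event-free patients remain and the denominator shrinks:

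per-protocol rate = p / (1 − e).

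| e (assumed) | p = 25% | p = 55% | Randomized for 60 evaluable, 60/(1 − e) |
|---|---|---|---|
| 5% | 26.3% | 57.9% | 64 |
| 10% | 27.8% | 61.1% | 67 |
| 20% | 31.3% | 68.8% | 75 |

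**Upper bound.** Assume exponential PFS and that every failure before week 12 is excluded. With the 6-month assessment at week 24, PFS at week 12 is √p, so the per-protocol rate is p/√p = √p: 25% becomes 50% and 55% becomes 74%. Taking six calendar months instead gives 47% and 72%. The scan timing above makes this bound unrealistic.

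**Effect on the arm contrast.** Take a true 25% in both arms, all excluded patients failures, and 30 analysed per arm. The last column is the exact binomial rejection probability of the one-sided pooled z-test at 0.10.

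| Excluded, Arm 1 / Arm 2 | Per-protocol rates | Difference (Arm 2 − Arm 1) | One-sided rejection |
|---|---|---|---|
| 0% / 0% | 25.0% / 25.0% | 0 | 10.5% |
| 10% / 20% | 27.8% / 31.3% | +3.5 points | 17.0% |
| 20% / 10% | 31.3% / 27.8% | −3.5 points | 6.1% |

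The contrast can also shrink when there is a true effect. In the upper bound with six calendar months, 25% vs 55% becomes 47% vs 72%, and the gap falls from 30 to 25 points.

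**If the excluded are not failures.** If 5% or 10% of patients are excluded and all of them would have been event-free, 25% falls to (0.25 − 0.05)/0.95 = 21.1% or (0.25 − 0.10)/0.90 = 16.7%.

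**The case against.** The strongest reply is that the primary result is not exposed. ITT contains every randomized patient and is the primary population, so a patient found unevaluable stays in it. Conditioning on compliance is what a per-protocol set is for, and reporting one beside ITT is conventional. A detailed SAP is still to be written before the final analysis. All of this stands, and it limits the point to the per-protocol analyses.

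Three stronger readings are tempting, and the documents do not support them.

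- *Every per-protocol result is biased upward.* Single-arm rates rise only if the excluded patients are mostly failures. The contrast has no fixed sign, and neither do correlative results. Section 8 keeps patients who stop for toxicity on study with radiographic data collected, and suggests that benefit may accompany autoimmune toxicity, so these patients need not be failures.
- *Patients who progress drop out of the set.* Scheduled imaging starts at week 12, progression there does not end treatment by itself, and stopping for PSA rise alone is discouraged. Eligibility also requires a life expectancy of at least 6 months and excludes rapidly progressive symptomatic disease. The 3-month median describes progression, not stopping treatment.
- *Replacing unevaluable patients creates the bias.* Randomizing more patients adds to ITT and removes nobody. The exclusion does the harm; over-enrolment only lets the selected set decide when accrual ends.

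What remains is that the rule as written does remove early deaths and symptomatic progressions, and nothing in the plan restores them to the per-protocol analyses.

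**Conclusion.** The point holds for the per-protocol analyses only. Their membership depends on a post-randomization condition that early failure can break, which tends to raise per-arm PFS rates and can move the arm contrast up or down. With 5 to 20% of randomized patients excluded and all of them failures, the gain is about 1 to 6 points on a true 25% and 3 to 14 points on a true 55%. Both the exclusion range and the assumption that all are failures are mine, because the documents give neither. The real effect is probably modest, since purely radiographic failures can remain in the set. The primary ITT result is not touched by this rule. This is an inexpensive improvement to a supportive analysis and does not threaten the trial's main conclusion.

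**What to change.** In Analysis Populations, define per-protocol as eligible patients who received the assigned treatment with adequate compliance up to week 12 or until progression, death or treatment-related toxicity, whichever comes first. Early deaths and progressions then count as failures, and patients who stop for toxicity are analysed by their actual outcome, for which Section 8 already keeps data collection going. State that the per-protocol analysis is supportive of ITT, and report the number excluded by arm and by reason.

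The cost is one sentence of definition, one table, a little more analysis work and slightly less favourable per-protocol rates. The accrual rule need not change for this purpose.
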